## PROTOCOL

This study implements a standardized protocol for NMBD (neuromuscular blocking drug) management that is currently used by some providers at UWMC and HMC to help prevent residual paralysis in surgical patients. While this protocol is within the scope of routine care that an anesthesiologist could follow in his/her clinical practice, it is not consistently used throughout HMC. This protocol follows clinical best practices for NMBD management in a surgical population and adheres to the recommendations from the P&T committee on reversal drug choice and recommendations from the Department of Anesthesiology and Pain Medicine on neostigmine dosing. While this protocol is in line with best practices, we are continuing to systematically evaluate it in the setting of prospective research. All drugs will be administered for clinical care only. This research does not add additional medications. The study will take place at HMC and will follow a standardized research protocol for the timing, dosing, and monitoring surrounding muscle relaxants and reversal, and makes use of objective TOF monitors. If a patient agrees to participate in this study, the following research protocol will occur:

### Before Surgery:

1. **TOF measurements before surgery:** A study investigator will perform the routine clinical train-of-four measurements with an objective monitor at baseline after the clinical induction of general anesthesia but before the administration of the NMBD. Information will be recorded for research purposes. Research staff will leave the operating room after obtaining the baseline measurement and will return to the operating room at the end of the surgical procedure, to be available for TOF ratio measurements at the time of extubation.
2. **Dose calculation of initial NMBD:** A study investigator will assist the anesthesia provider with calculation of the recommended intubating dose of rocuronium (an NMBD). The dose will be calculated per this research protocol based on Ideal Body Weight (IBW) which is calculated as follows:
  - a. For women 45.5 kg plus 2.3 kg/inch over 5 feet of height
  - b. For men 50 kg plus 2.3 kg/inch over 5 feet of height.
  - c. For routine intubations, the recommended dose for intubation will be a maximum of Rocuronium 0.6 mg/kg.
  - d. The intubating dose will be reduced by 15% for females
  - e. Higher intubating dose may be used at the discretion of the anesthesia provider

### During Surgery:

3. **Additional dose calculation of NMBD:** Each additional dose of rocuronium will be 25% of the recommended intubating dose and will be administered when the TOF count has returned to at least 2, the aim is to maintain an intraoperative TOF count of 1-2 unless the anesthesia provider has deemed deep paralysis to be necessary in which case a TOF count of 0 will be maintained. An attempt will be made to avoid administration of rocuronium during the last 30 minutes of the procedure. If the surgeon requests muscle relaxation during the final stage of surgery, consideration should be given to providing relaxation by using non-NMBDs such as propofol which is an option an anesthesiologist has in their clinical practice.

After Surgery: Patients will receive reversal drugs for their routine care that will help reverse the effects of their muscle relaxant. In this study, the decision of reversal drug use will follow institutional guidelines. The timing and dose calculation of the reversal drug will follow the research protocol as follows:

4. **Timing of neostigmine or sugammadex:** Based on the results of the clinical pre-reversal TOF assessment, reversal with neostigmine will be administered only if the objective TOF-ratio is between 40%-90%. If the block is deeper than this, then sugammadex will be used for reversal (This is per institutional guidance on choice of reversal drug).
5. **Dose calculation of neostigmine and sugammadex:** For this study, the dose of neostigmine will be calculated based on the IBW. The dose of sugammadex will be calculated based on patients' actual body weight.  
\*For all subjects enrolled in this study, we will follow a dose schedule which is based on clinical TOF monitoring and is in accordance with institutional recommendations for dosing of neostigmine.
6. **Timing of extubation:** The patient's trachea will not be extubated before routine objective monitoring confirms recovery to a TOF-ratio  $\geq 90\%$ . However, in the case that objective monitoring cannot be obtained by the provider then the following will happen:
  - a. For subjects who receive neostigmine for their routine care , it is recommended that the patient's trachea will not be extubated earlier than 10 minutes after the administration of this drug.
  - b. For subjects who receive sugammadex for routine care, it is recommended that the patient's trachea will not be extubated earlier than 3 minutes after drug administration.
7. **TOF measurements after surgery (extubation):** The TOF-ratio will be measured by a study investigator or provider at the time of extubation. Information will be recorded for research purposes. If we miss obtaining research measurements at the time of extubation, we will obtain TOF measurements on the patient's arrival to the PACU.
8. **Collection of data from EMR:** We will collect information from the patient's medical record including the intraoperative TOF counts, ASA class, surgical procedure, times of the surgical procedure, time and dose of administered medications, and the patient's temperature in the operating room and PACU.

### **Statistical analysis**

We present descriptive statistics [mean (standard deviation) or frequencies] for baseline measures of patient and surgery characteristics. The primary endpoint, incidence of PRNB ( $n\text{TOFR} < 0.9$ ) on arrival to the PACU, was calculated with exact binomial 95% confidence interval, and graphically displayed using scatterplots. The primary analysis was “per-protocol” and patients were excluded if the protocol was not followed. Secondary endpoints included severe PRNB, defined as  $n\text{TOFR} < 0.7$  on arrival to the PACU, and PRNB at time of tracheal extubation ( $n\text{TOFR} < 0.9$ ). These were also calculated with the exact confidence intervals. Additionally, we calculated the incidence of severe PRNB at time of tracheal extubation and the incidence of PRNB using raw (non-normalized) measurements.

We compared the duration between end of surgery and arrival to the PACU for patients whose tracheas were extubated in the OR and those extubated in PACU. We also compared the duration between end of surgery and arrival to the PACU for patients receiving sugammadex or neostigmine.

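### The primary PRNB incidence is estimated only after excluding patients who departed from the protocol, with no estimate regardless of adherence, and exclusion can depend on the TOF ratio before extubation

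*SAP*

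**What the plan says.** The primary endpoint in the SAP (Statistical analysis) is a normalised TOF ratio (nTOFR) below 0.9 at PACU arrival, reported as one proportion with a 95% exact binomial interval. On the analysis set, the SAP says: "The primary analysis was “per-protocol” and patients were excluded if the protocol was not followed". The other PRNB analyses change the cut-off, the time point or the normalisation. None is described as using a wider set, and the set for the secondary endpoints is not stated.

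Protocol item 6 (Timing of extubation) is firmly worded when a monitor is available: the "trachea will not be extubated before routine objective monitoring confirms recovery to a TOF-ratio" of at least 90%. It has an exception: "in the case that objective monitoring cannot be obtained by the provider then the following will happen". Waiting times then apply, as recommendations. For neostigmine, "it is recommended that the patient's trachea will not be extubated earlier than 10 minutes after the administration of this drug"; item 6b has the same form for sugammadex, with 3 minutes.

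Two other steps leave room for discretion. Item 2e says "Higher intubating dose may be used at the discretion of the anesthesia provider", and item 3 says "An attempt will be made to avoid administration of rocuronium during the last 30 minutes of the procedure".

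On the PACU-arrival reading, item 7 says: "If we miss obtaining research measurements at the time of extubation, we will obtain TOF measurements".

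**The concern.** The exclusion is applied after enrolment, on the basis of how the case was managed. One of the rules that defines proper management is itself a TOF threshold, and the endpoint is also a TOF threshold. On a literal reading, a monitored patient extubated below 90% has departed from the protocol and leaves the analysis. The set in which PRNB is counted can therefore depend on a measurement closely related to PRNB.

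The protocol's introduction presents the study as an evaluation of a standardised way of managing neuromuscular block. Incidence when the protocol is followed is a legitimate answer to one question. Alone, it does not show what happened in everyone managed under the protocol, including cases where it could not be, or was not, carried through. The exact interval covers sampling error only, not the choice of who is counted. With no second estimate and no account of the exclusions, a reader cannot tell how far the reported incidence depends on that choice.

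**Working it through.** **Figures in the plan.** The available text gives no sample size, number excluded or PRNB rate, so there is nothing to reproduce. The first step is a reading of the text. The second is arithmetic on assumed inputs.

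**Step 1: where exclusion and outcome meet.**

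- *PRNB at extubation (secondary).* The event is nTOFR below 0.9 at extubation. Extubating a monitored patient below a TOF ratio of 90% breaches item 6. Apart from normalisation, the event and the breach nearly coincide. If the per-protocol set is used here, the exclusion acts almost directly on the outcome. The SAP does not say whether it is.
- *PRNB at PACU arrival (primary).* The reading usually comes after extubation and is normalised, whereas item 6 does not mention normalisation. A patient who met item 6 can still be counted as PRNB, and one who did not may have recovered by arrival. The two are related but not the same.
- *Where the link does not apply.* Patients without objective monitoring fall under the waiting-time exception. The SAP also compares "patients whose tracheas were extubated in the OR and those extubated in PACU"; for those extubated in the PACU, the arrival reading precedes extubation.

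**Step 2: what the difference depends on.** Let s be the excluded share of measured patients, p_adh the PRNB rate in adherers and p_exc the rate in those excluded.

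- Per-protocol incidence = p_adh
- All-measured incidence = (1 − s) × p_adh + s × p_exc
- Difference (per-protocol minus all-measured) = s × (p_adh − p_exc)

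Both inputs are assumed: s = 5, 10 or 20%, and a rate difference of 0, 10 or 20 points in either direction.

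| s | rate difference 10 points | rate difference 20 points |
|---|---|---|
| 5% | ±0.5 points | ±1.0 points |
| 10% | ±1.0 points | ±2.0 points |
| 20% | ±2.0 points | ±4.0 points |

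If the two rates are equal, the difference is zero at any s.

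**Worked case (assumed).** 100 measured patients with 10 events give 10/100 = 10.0% (95% exact interval 4.9 to 17.6). Twenty are excluded.

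| Events among the 20 excluded | Per-protocol incidence (95% exact interval) | Difference from all-measured |
|---|---|---|
| 0 | 10/80 = 12.5% (6.2 to 21.8) | 0.20 × (12.5 − 0) = +2.5 points |
| 2 | 8/80 = 10.0% (4.4 to 18.8) | 0.20 × (10 − 10) = 0 |
| 4 | 6/80 = 7.5% (2.8 to 15.6) | 0.20 × (7.5 − 20) = −2.5 points |

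The arithmetic limits, which are not expected values, are 12.5% (no event excluded) and 0/80 = 0% (0 to 4.5) if all 10 events are among the excluded.

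**The case against.** The strongest reply has four parts.

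*Per-protocol is a coherent choice.* The study estimates one proportion, and the available text describes no randomised comparison that an all-patient set would protect. The SAP states its choice openly. This stands, and it is why the per-protocol analysis should be kept and the second estimate can be a supporting one.

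*No bias is shown.* A reader might infer that the per-protocol figure understates PRNB, because patients extubated too early are removed. The documents do not support that. They do not say which departures led to exclusion, how many there were, or what those patients' readings were. The item 6 threshold is not stated as normalised, the primary reading is usually later, and the link does not apply to some patients. This stands: direction and size are open.

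*The discretionary wording is less of a problem than it looks.* A reader might infer that adherence cannot be determined at all. That goes too far. Item 2e permits a higher dose, so using one follows the protocol. Item 3 asks for an attempt, and an attempt satisfies it. Items 6a and 6b are recommendations. The 90% threshold with a monitor and the TOF range for neostigmine are firm. What remains is narrower: the SAP does not say whether departing from a recommendation-only step led to exclusion.

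*The wider estimate may be selective too.* It needs a PACU-arrival reading, and item 7 plans one only when the extubation reading is missed. This also stands, so the number without a reading must be reported.

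None of this supplies the missing estimate.

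**Conclusion.** The point holds in a limited form. The SAP applies a post-enrolment exclusion to its primary estimate, the available text plans no estimate without it, and item 6 means that exclusion can depend on a variable related to the outcome. The exposure is greatest for PRNB at extubation, conditional on the same set being used there, and weaker for the primary endpoint.

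The size is unknown. The range of 0.5 to 4.0 points in either direction, or zero with equal rates, rests wholly on assumed exclusion shares and rate differences. It shows what the result depends on, not what happened in this study. The conclusion also rests on a literal reading of item 6 as a condition of adherence and on the text available, since some pages of both documents were removed. It should be fixed because the reader cannot otherwise assess the headline figure; it is not evidence that the figure is wrong.

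**What to change.** Keep the per-protocol analysis and label it as PRNB incidence when the protocol is followed. Then:

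1. Add, as a supporting analysis, PRNB incidence with a 95% exact binomial interval in all enrolled patients who received rocuronium and have a PACU-arrival reading, regardless of adherence.
2. Do the same for PRNB at extubation among patients with an extubation reading, and state the set used for each secondary endpoint.
3. Tabulate the excluded patients by reason, with their nTOFR, and say whether departing from a recommendation-only step (items 3, 6a and 6b) led to exclusion.
4. Report how many patients have no PACU-arrival reading. Reconciling item 7 with the primary endpoint is a separate point.

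The cost is one more proportion per endpoint, a short table and a few lines of SAP text. The headline may look less favourable beside the added figure. The added set is limited to patients with readings and may itself be selective. The SAP is written in the past tense, so it may be too late to classify departures without knowledge of the PACU reading, but the counts, reasons and extra proportions can still be reported.
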